Cover Page for Protocol

Document: Protocol

Official Study Title: Comparison of Myocardial Blood Flow Measurements with Dedicated Solid State SPECT Camera Imaging versus PET Imaging

Document Date: August 2, 2018

NCT: NCT02280941

**Comparison of Myocardial Blood Flow Measurements with Dedicated Solid State
SPECT Camera Imaging
versus PET Imaging**

Principal Investigator: [name], FRCPC

Co-Investigators:
[name], FRCPC
[name], PhD
[name]
[name]

Study Centre

The University of Ottawa Heart Institute at the Ottawa Hospital

Study Funding Support

GE Healthcare,
Global Research Headquarters
[name],
[name]

Protocol Version 4: August 2, 2018

Contents

Clinical Protocol Synopsis	5
Abbreviations	8
1.1 Background and Rationale	9
1.2 Hypothesis	10
2. Study Objectives	10
3. Study Design	10
5. Sample Size and Statistical Analysis	12
6. Study Population	13
6.1 Source of Participants	13
6.2 Inclusion Criteria	13
6.3 Exclusion Criteria	13
6.4 Withdrawal from Study	14
6.5 Early Termination	14
7. Data Collection	14
7.1 Demographic Information	14
7.2 Medical History	14
7.3 Clinical Status	14
7.4 Caffeine Ingestion	14
7.5 Pregnancy Assessment	15
8. Risk Benefit Assessment	15
8.1 SPECT and PET Imaging	15
8.2 Dipyridamole Pharmacological Stress	15
9. Safety and Tolerability	15
9.1 Safety Variables	15
9.2. Safety Reporting	16
9.3 Pregnancy	16
10. Study Records	16
10.1 Investigator Study Files	16
10.2 Participant Clinical Trial Files	16
11. Monitoring/Access to Files for Inspection	16

12. Publication.....	17
13. Budget.....	17
13.1 Budget Details.....	Error! Bookmark not defined.
14. References.....	18

Clinical Protocol Synopsis

Study Title: Comparison of Myocardial Blood Flow Measurements with Dedicated Solid State SPECT Camera Imaging versus PET Imaging

Version 4: August 2, 2018

Study Centre

University of Ottawa Heart Institute

Study Objectives

1. To evaluate the correlation of global and regional myocardial blood flow (MBF) measurements and calculated myocardial flow reserve (MFR) using single photon emission computed tomography (SPECT) and ^{99m}Tc -tetrofosmin (^{99m}Tc) to positron emission tomography (PET) with Rubidium-82 (Rb-82) or N-13-ammonia ($^{13}\text{NH}_3$) in patients with an intermediate to high probability of CAD (Phase 1);
2. To determine the reproducibility of global and regional myocardial blood flow measurements and calculated myocardial flow reserve using SPECT and ^{99m}Tc -tetrofosmin in patients with an intermediate to high probability of CAD (Phase 2);
3. To evaluate the correlation of global and regional myocardial blood flow measurements and calculated myocardial flow reserve using SPECT and ^{99m}Tc -tetrofosmin to PET with Rb-82 or $^{13}\text{NH}_3$ in normal volunteers (Phase 3).

Hypotheses

1. The correlation of global and regional myocardial blood flow measurements and calculated myocardial flow reserve using SPECT to PET in patients with an intermediate to high probability of CAD will be $r > 0.6$ (Phase 1);
2. The test-retest reproducibility of global and regional myocardial blood flow measurements and calculated myocardial flow reserve using SPECT in patients with an intermediate to high probability of CAD will be within 10 to 15% (Phase 2);
3. The correlation of global and regional myocardial blood flow measurements and calculated myocardial flow reserve using SPECT to PET in normal volunteers will be $r > 0.6$ (Phase 3).

Study Type

Investigator-initiated, imaging research.

Study Design

For the Phase 1 correlation study, participants will undergo a standard clinical rest/stress PET study with either Rb-82 or $^{13}\text{NH}_3$ with a low dose CT and a rest/stress SPECT study with $^{99\text{m}}\text{Tc}$ within a 4 week period. Participants with CAD will be recruited from patients already referred for clinical SPECT or PET imaging and with an intermediate to high probability of CAD. Any participants who have an intervention or undergo a significant cardiac event during the 4 week interval will be excluded.

For the Phase 2 reproducibility study, participants will be recruited from patients already referred for clinical rest/stress SPECT imaging and with an intermediate to high probability of CAD. Participants will undergo a second rest/stress SPECT with $^{99\text{m}}\text{Tc}$ within a 4 week period. Any participants who have an intervention or undergo a significant cardiac event during the 4 week interval will be excluded.

For the Phase 3 correlation study, normal volunteer participants will undergo a standard rest/stress PET study with either Rb-82 or $^{13}\text{NH}_3$ with a low dose CT and a rest/stress SPECT study with $^{99\text{m}}\text{Tc}$ within a 4 week period.

Number of Participants

For the correlation studies (hypothesis 1 and 3), two specific populations including 1) 30 participants with an intermediate to high probability of CAD (Phase 1) and 2) 30 healthy volunteers without known heart disease (Phase 3).

For the reproducibility study (hypothesis 2), 30 participants with an intermediate to high probability of CAD (Phase 2).

Inclusion and Exclusion Criteria**Inclusion Criteria****For all participants**

- Age \geq 18 years old
- BMI \leq 40 kg/m²
- Able and willing to comply with the study procedures

1. Participants with an intermediate to high probability of CAD
 - Suspected or known CAD on a stable medication regime
2. Healthy volunteers without known heart disease OR
 - Low risk of CAD (ACC Guidelines Pre-test Probability of CAD by Symptoms, Gender and Age)

Exclusion Criteria:

- History or risk of severe bradycardia (heart rate < 50 beats per minute) not related to chronotropic drugs

- Known second- or third-degree AV block without pacemaker
- Dyspnea (NYHA III/IV), wheezing asthma or severe COPD
- Coronary artery bypass graft (CABG) surgery within 60 days prior to screening or at any time after consent
- Percutaneous coronary intervention (PCI) within 30 days prior to screening or at any time following consent
- Acute myocardial infarction or acute coronary syndrome within 60 days prior to screening or at any time following consent
- Recent use of dipyridamole-containing medications (e.g. Aggrenox)
- Known hypersensitivity to dipyridamole
- Breastfeeding or pregnancy
- Claustrophobia or inability to lie still in a supine position
- Unwillingness or inability to provide informed consent

Study Duration for Participants Duration of participation is a maximum of 4 weeks. No changes to clinical care in the CAD population will be made.

Safety and Tolerability Safety variables will include the recurrence of procedure related adverse events. Adverse events (AE) and serious adverse events (SAE) will be defined and reported according to regulatory standards. AEs and SAEs will be reported from the signing of the consent and followed until resolution or determined to be not clinically significant.

Statistical Methods For the correlation studies, global and regional MBF measurements acquired using SPECT and PET and calculated MFR measurements will be correlated with Spearman correlation analysis. For the reproducibility study, Bland-Altman plots will be used to determine significant bias and the coefficient of repeatability of global and regional MBF measurements acquired using SPECT and calculated MFR.

Abbreviations

3D	three dimensional
ACC	American College of Cardiology
AC	attenuation correction
AE	Adverse Event
AV	atrial-ventricular
BMI	body mass index
CABG	coronary artery bypass graft
CAD	coronary artery disease
CRF	case report form
COPD	chronic obstructive pulmonary disease
CT	computed tomography
g	gram
ICH GCP	International Conference on Harmonization Good Clinical Practice
kg	kilograms
kVp	kilo-volt potential
MBF	myocardial blood flow
MBq	megabequerels
mcg	micrograms
mCi	millicurie
MFR	myocardial flow reserve
mg	milligrams
min	minute
mm	month
MRN	medical record number
mSv	milliseverts
¹³ NH ₃	Nitrogen-13-ammonia
NC	no correction
NYHA	New York Heart Association
OHSN-REB	Ottawa Health Science Network Research Ethics Board
PET	positron emission tomography
PCI	percutaneous coronary intervention
PHI	Personal Health Information
⁸² Rb	Rubidium-82 Chloride
SAE	Serious Adverse Event
SC	scatter correction
SPECT	single photon emission computed tomography
SOP	Standard Operating Procedures
^{99m} Tc	Technetium-99m
²⁰¹ Tl	Thallium Chloride
TOH	The Ottawa Hospital
UOHI	University of Ottawa Heart Institute
yyyy	year

1. Introduction

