For the first time, [name] and our group recently demonstrated the accurate quantification of MBF in a pig model of rest and transient occlusion at stress [15]. Data were acquired using attenuation and scatter corrected dynamic SPECT data with a NM 530c camera with ^{201}TI , $^{99\text{m}}\text{Tc}$ -tetrofosmin and $^{99\text{m}}\text{Tc}$ -sestamibi. MBF was measured with gold-standard microspheres injected simultaneously with the SPECT tracers. Measured extraction fraction data agreed with those obtained previously using invasive techniques. MBF determined using the measured extraction fractions produced accurate values and good correlations with microsphere MBF between $r=0.75$ and $r=0.83$ ($p<0.01$ for all) and the resulting correlation in the MFR was up to 0.89 ($p<0.01$). Thus, non-invasive measurement of absolute MBF with a stationary dedicated cardiac SPECT is feasible using common perfusion tracers.

The goal of this study is to compare SPECT and PET measurement of MBF and MFR and determine the reproducibility of SPECT MFR measurements in patients.

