1.2 Hypothesis

1. The correlation of global and regional myocardial blood flow (MBF) measurements and calculated myocardial flow reserve (MFR) using SPECT to PET in participants with an intermediate to high probability of CAD will be $r > 0.6$ (Phase 1);
2. The test-retest reproducibility of global and regional MBF measurements and calculated MFR using SPECT in participants with an intermediate to high probability of CAD will be within 10 to 15% (Phase 2);
3. The correlation of global and regional MBF measurements and calculated MFR using SPECT to PET in normal volunteers will be $r > 0.6$ (Phase 3).

2. Study Objectives

1. To evaluate the correlation of global and regional MBF and MFR measured using SPECT to that measured using PET in participants with an intermediate to high probability of CAD (Phase 1);
2. To determine the reproducibility of global and regional MBF measurements and calculated MFR using SPECT in participants with an intermediate to high probability of CAD (Phase 2);
3. To evaluate the correlation of global and regional MBF and MFR measured using SPECT to that measured using PET in normal volunteers (Phase 3).

3. Study Design

Phase 1:

Patients referred to the University of Ottawa Heart Institute Diagnostic Imaging Department for myocardial perfusion imaging (MPI), PET or SPECT, will undergo a clinically indicated rest/stress PET scan using either Rb-82 or $^{13}\text{NH}_3$. Research imaging will consist of a rest/stress SPECT scan with $^{99\text{m}}\text{Tc}$ completed with 4 weeks of the PET scan, occurring either before or after the PET scan.

Study end will be defined as the completion of both the PET and SPECT scans.

Phase 2:

Patients will undergo a clinically indicated rest/stress SPECT scan as referred. Research imaging will consist of a second rest/stress SPECT scan with $^{99\text{m}}\text{Tc}$ within 4 weeks of the clinical SPECT scan.

Study end will be defined as the completion of both SPECT scans.

Phase3:

Normal volunteers will undergo a rest/stress PET scan using either Rb-82 or $^{13}\text{NH}_3$ and a rest/stress SPECT scan with $^{99\text{m}}\text{Tc}$ completed within a 4 week period.

Study end will be defined as the completion of both the PET and SPECT scans.

4. SPECT and PET Imaging

4.1 $^{99\text{m}}\text{Tc}$ SPECT Imaging

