Rb-82 or $^{13}\text{NH}_3$ PET Imaging will be performed according to the UOHI standard clinical protocol [18]. Briefly, the participants will be positioned in a 3D PET system (GE Discovery 690 PET/VCT). The initial rest PET scan will include a low-dose CT for attenuation correction (0.4 mSv; fast helical 2 s, 120 kVp with axial and angular mA-modulation at noise-index = 50). Hyperemic stress flow will be induced with dipyridamole (0.14 mg/kg/minute for 5 minutes). PET imaging will be performed using 1000 MBq (0.73 mSv) of Rb-82 or 3 MBq/kg (0.7 mSv) of $^{13}\text{NH}_3$ at rest and during stress with radiotracer injected 8 minutes following the start of dipyridamole infusion. MBF and MFR will be quantified and polar-maps generated for each rest and stress state using in-house FlowQuant[®] software [17] as well as Infinia (GE Canada).

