4.3 Concentration of $^{99\text{m}}\text{Tc}$ SPECT tracer

SPECT perfusion tracers are known to bind to red blood cells limiting the amount of tracer available to the myocardium for extraction [15]. Thus, concentration function used in the kinetic analysis is better represented by the plasma concentration of tracer instead of the whole blood concentration, as measured by the image-based methods used in this study. Correction for the plasma to whole blood ratio can be done by applying a correction curve. The correction curve has been determined with pig experiments but needs to be calibrated to humans. To estimate this correction, we will measure the whole-blood to plasma tracer concentration ratio at equilibrium (~30min post injection) which will then be used to rescale the full curve that was measured in the pig study. For this purpose, a 12ml blood sample (2x6ml) at 30min after the rest tracer injection and a 2nd 12ml (2x6ml) blood sample at 30min will be drawn after the stress injection. Whole blood and serum aliquots will be prepared and then measured in a well-counter to determine the concentration ratio.

5. Sample Size and Statistical Analysis

The sample size for the correlation studies (hypotheses 1 and 3) was calculated to provide a 95% confidence interval around $r=0.6$ that excludes $r=0.25$, which is considered the upper bound of no correlation. To obtain a difference in the z-transform of $r=0.6$ and $r=0.25$ of 1.96 requires an n of 24. A withdrawal rate of 10 to 15 % increases the number of patients required to 30 per group.

The sample size for the reproducibility study (hypothesis 2) is estimated to detect a 10% difference on background of 15% variability (assuming a SPECT MBF uncertainty similar to the high end of PET variability). This requires a sample size of 26 (power = 0.95; alpha =0.05). A withdrawal rate of 10 to 15 % increases the number of patients required to ~ 30 per group.

Adverse events will be listed on an individual basis. All safety variables and demographic data will be tabulated with descriptive statistics, if appropriate.

For the correlation studies global and regional MBF measurements acquired using SPECT and PET and calculated MFR will be correlated with Spearman correlation analysis. For the reproducibility study Bland-Altman plots will be used to determine significant bias and the coefficient of repeatability of global and regional MBF measurements acquired using SPECT and calculated MFR.

6. Study Population

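### The Spearman and Bland-Altman plans do not fix the unit of analysis; pooling rest with stress, or regions as if independent, could mislead on MBF

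*Combined protocol and SAP*

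**What the plan says.** The correlation analysis for Phases 1 and 3 is one sentence in the synopsis (Statistical Methods): "global and regional MBF measurements acquired using SPECT and PET and calculated MFR measurements will be correlated with Spearman correlation analysis". Section 5 repeats it without further detail. Section 1.2 sets a single target: "The correlation of global and regional MBF measurements and calculated MFR using SPECT to PET in normal volunteers will be" above 0.6 in Phase 3, with the same threshold for Phase 1.

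For Phase 2, Section 5 states that "Bland-Altman plots will be used to determine significant bias and the coefficient of repeatability of global and regional MBF measurements", and the same for MFR. It names no test for bias.

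Section 3 gives every participant rest and stress imaging at each scan. Section 4.2 has PET "polar-maps generated for each rest and stress state". That describes image processing and sets no rule for the correlation.

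Section 5 sizes the correlation studies at 24, raised to 30 per group for withdrawals, so that a 95% interval around 0.6 excludes 0.25.

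The documents do not define the regions or their number. They also do not say whether rest and stress MBF enter one coefficient, or how several values from one participant are handled.

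**The concern.** Each participant gives at least two global MBF pairs, one at rest and one at stress, and more once regions are counted. An ordinary Spearman coefficient or Bland-Altman analysis takes its pairs as independent and from one population. Two things can go wrong if an analyst puts all values in together.

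- **States.** Dipyridamole is given to raise flow, so stress values lie above rest values on both modalities. That shift creates a rank correlation even if SPECT cannot rank patients by flow within either state. A camera that merely separates rest from stress could then be reported as agreeing with PET on MBF.
- **Regions.** Values from one heart are correlated. Counting each region as a new observation overstates the information, so correlation intervals are too narrow and a regional bias test is too often positive.

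MFR is already a stress/rest ratio, so it cannot be affected by pooling states. What is at stake is the MBF conclusion and the regional conclusions.

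**Working it through.** **1. The plan's own figure.** Fisher z: n = (1.96 / (atanh 0.6 − atanh 0.25))² + 3 = (1.96 / (0.6931 − 0.2554))² + 3 = 23.05, rounded up to 24. This reproduces Section 5. The formula is for independent pairs, and the result is then inflated as a number of patients, so it implies one pair per participant.

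**2. Pooling rest and stress, no patient-level association.** The documents give no stress/rest ratio or spread, so these inputs are assumptions: lognormal flow, the same relative spread (CV) in both states, and SPECT independent of PET within each state.

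- Log-scale SD: s = √ln(1 + CV²). At CV 30%, s = 0.294.
- Separation: d = ln(ratio) / s.
- Chance that a stress value exceeds a rest value: p = Φ(d/√2).
- Large-sample pooled Spearman: 3(p_SPECT − 0.5)(p_PET − 0.5). With complete separation p = 1, giving the ceiling 3 × 0.25 = 0.75.

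The last column comes from simulation with 26 participants (10,000 runs). This is about what remains of 30 after 15% withdrawal (30 × 0.85 = 25.5).

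| Ratio, SPECT / PET (30% spread) | p, SPECT / PET | Pooled Spearman | Trials above 0.6 |
|---|---|---|---|
| 1.5 / 1.5 | 0.836 / 0.836 | 0.34 | 1% |
| 2.0 / 2.0 | 0.953 / 0.953 | 0.61 | 60% |
| 2.5 / 2.5 | 0.986 / 0.986 | 0.71 | 98% |
| 1.5 / 2.0 | 0.836 / 0.953 | 0.46 | 8% |

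For equal ratios of 1.5, 2.0 and 2.5, a 20% spread gives 0.55, 0.73 and 0.75, and a 40% spread gives 0.22, 0.48 and 0.62. Whatever the ratio, 0.6 needs a separation of about 2.3 within-state SDs on both modalities. At 1 SD pooling gives only about 0.20.

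In the same trials, rest alone, stress alone or MFR exceeds 0.6 about 0.1% of the time.

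**3. Regions as independent pairs: correlation interval.** The region counts (3 and 17) and within-patient correlations are assumed. With equal regional means, 26 participants and a true Spearman of 0.6, a naive 95% interval covers as follows.

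| Within-patient correlation | 3 regions | 17 regions |
|---|---|---|
| 0.5 | 91% | 66% |
| 0.7 | 86% | 52% |
| 0.9 | 79% | 42% |

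**4. Regions as independent: Phase 2 bias test.** With k regions and within-patient correlation ρ of the differences, the variance of the mean is larger than the naive value by D = 1 + (k − 1)ρ. A nominal 5% test then rejects with probability of about 2[1 − Φ(1.96/√D)].

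- k = 3: ρ = 0.1 gives D = 1.2 and 7%; ρ = 0.9 gives D = 2.8 and 24%.
- k = 17: ρ = 0.1 gives D = 2.6 and 22%; ρ = 0.9 gives D = 15.4 and 62%.

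Simulation agrees: about 7% to 25% and 23% to 62%. A test on participant means stays near 5%.

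**The case against.** The strongest reply is that nothing in the plan says values are pooled, and several features point the other way. The sizing implies one pair per participant, PET maps are made per state, and MFR cannot be calculated unless the states are kept apart. This is fair. A reader might infer that the plan pools rest and stress; the documents do not support that. They leave the unit of analysis open, because none of these features is a rule for the MBF correlation.

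A reader might also infer that pooling could deliver the study's stated hypothesis. It could not, because Section 1.2 covers MBF and MFR together, and MFR would stay near zero if there were no patient-level association. The exposure is a separate MBF statement that conflicts with the MFR result.

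The pig correlations in Section 1.1 (0.75 to 0.83) might be taken as a sign that the group pools states. That section names three tracers, and the range can equally be one value per tracer, so it shows nothing either way.

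For regions, one might infer that pooling also raises the coefficient. That needs regional mean flows to differ in the same direction on both modalities, on which the documents are silent. With equal means and no association, the pooled coefficient averages 0.00. The regional point is therefore about precision and false positives.

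Finally, the Phase 2 error rates apply only to a naive test, and the plan names none. That stands as a condition on the figures.

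**Conclusion.** The concern holds as a gap in specification with a possible material effect. One permitted reading of the plan, pooling states, can bring the MBF correlation to about 0.6 or above with no patient-level association. Under the assumed inputs the result runs from 0.22 to 0.75, so the effect may be decisive or modest. It is smaller when the modalities respond differently. Pooled regions would give intervals that are too narrow, and a naive regional bias test could have several times its nominal 5% error. All ratios, spreads, region counts and within-patient correlations are assumptions. The n of 24 is correct for one pair per participant. The change should be made before analysis; confidence is medium, because the harm depends on how the analyst reads the text.

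**What to change.** Amend Section 5 and the synopsis.

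(a) Compute Spearman separately for rest MBF, stress MBF and MFR, with one global value per participant, which matches the sizing. Name the correlation to which the 0.6 threshold applies as primary. Any coefficient that combines rest and stress is descriptive only.

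(b) Define the regions. Report regional correlations by region and state, or average the region-specific correlations with a bootstrap that resamples participants. Do not use a raw pool across regions.

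(c) For Phase 2, obtain regional bias and repeatability by state, with a participant-level bootstrap or a mixed model with a participant effect.

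The cost is a few sentences and some programming, with no extra scans. MBF correlations will probably be lower and regional intervals wider. The reason to name one primary is that requiring all three estimates to exceed 0.6 is strict. With 26 participants and a true Spearman of 0.6 for each, a single estimate passes about 48% of the time and all three together 16% to 18%.

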Following acquisition, the listmode data will be rebinned into 9x10s, 6x15s, 4x120s frames. The projection data for each frame will be independently reconstructed using manufacturer supplied MLEM iterative reconstruction that includes point-spread function modeling and a noise-suppression prior. A total of 30 iterations will be used corresponding to the manufacturer recommendation for resting (low-count) studies. Images will be filtered post-reconstruction using a 3D 5th-order Butterworth filter with a cut-off frequency of 0.37 cycles/cm. Images will be reconstructed without corrections (NC), and with attenuation correction (AC) and scatter correction (SC). When applied, AC will be based on the CT scan from the PET/CT acquisition which will be coregistered manually to the emission reconstruction using on-line quality assurance tools. SC will be applied to the projection data prior to reconstruction using a dual-energy window approach [15]. For the Phase 2 SPECT reproducibility study, an additional CT scan will be acquired on an Infinia/Hawkeye 4 SPECT/CT gamma camera and used in place of the CT from the PET/CT acquisition.

The reconstructed dynamic image series will be processed using FlowQuant (Ottawa, ON), our in-house kinetic analysis software [17] as well as Infinia (GE Canada). With this semi-automatic software, a 1-tissue-compartment model will be fit to the myocardium time-activity data to generate a parameterized map of the uptake rate constant K1 (ml/min/g) for the heart. K1 values will be scaled to MBF based on the K1-MBF relationship determined from the pig studies (15). Finally, the results from the FlowQuant (Ottawa, ON) will be compared to those of the commercially released Infinia software (GE Canada) to determine the similarities between the two software packages.

4.2 ^{82}Rb / $^{13}\text{NH}_3$ PET Imaging

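### Must the plan name one SPECT-PET correlation, software package and reconstruction to decide hypotheses 1 and 3?

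*Combined protocol and SAP*

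**What the plan says.** Section 1.2 and the synopsis put one threshold on a group of measures. For volunteers, Section 1.2 reads "The correlation of global and regional MBF measurements and calculated MFR using SPECT to PET in normal volunteers will be $r > 0.6"; the Phase 1 hypothesis in the synopsis is the same for patients, "using SPECT to PET in patients with an intermediate to high probability of CAD will be $r > 0.6$ (Phase 1". The Statistical Methods entry of the synopsis says that "global and regional MBF measurements acquired using SPECT and PET and calculated MFR measurements will be correlated with Spearman correlation analysis"; Section 5 says the same, and neither ranks the measures.

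Section 5 sizes the two correlation phases on a single coefficient: "To obtain a difference in the z-transform of $r=0.6$ and $r=0.25$ of 1.96 requires an n of 24". This is raised to 30 per group to allow for 10 to 15% withdrawal.

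The imaging sections produce several versions of each value. In Section 4.1, "Images will be reconstructed without corrections (NC), and with attenuation correction (AC) and scatter correction (SC"). The dynamic series goes through "our in-house kinetic analysis software [17] as well as Infinia (GE Canada"), and the section closes by saying the two packages will be compared for similarity. Section 4.2 uses both packages for PET as well, with "polar-maps generated for each rest and stress state".

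**The concern.** A numerical hypothesis should be decidable before the results are seen. Here each phase gives at least three global correlations (rest flow, stress flow, flow reserve) plus the regional ones. Two packages and two reconstructions turn the three into 3 × 2 × 2 = 12 global coefficients. The sample size speaks to one.

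If all must exceed 0.6, success is much less likely than for a single r. If any one were enough, success would be too easy. If the choice is left until afterwards, it could be made to suit the result. The choice of package is also sensitive because the funder makes one of the two.

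**Working it through.** **The plan's own figure.** Inputs from Section 5: r = 0.6, lower bound 0.25, z = 1.96.

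- atanh(0.6) − atanh(0.25) = 0.6931 − 0.2554 = 0.4377
- n = (1.96 / 0.4377)² + 3 = 20.05 + 3 = 23.05, rounded up to 24
- With withdrawal: 24 / 0.90 = 26.7, so 27; 24 / 0.85 = 28.2, so 29. The stated 30 covers both.

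The figure reproduces and is right for one correlation. It is a precision calculation: Section 5 states no power for hypotheses 1 and 3. At n = 24 and a true r of 0.6, even one coefficient meets the exclude-0.25 criterion in only about half of trials (50 to 51% by simulation with Spearman r).

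**What several correlations do.** The assumptions are not in the documents:

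- rest and stress analysed separately, one SPECT-PET pair per participant;
- Gaussian log flows and the same true Spearman r for rest flow, stress flow and flow reserve;
- rest-stress correlation of 0.3 or 0.6;
- 27 evaluable participants (30 less 10%).

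Share of simulated trials with observed r > 0.6, three global correlations:

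| True r | One chosen r | All three | At least one | Mixed verdict |
|---|---|---|---|---|
| 0.5 | 24% | 3% | 51–52% | 48% |
| 0.6 | 48–49% | 16–17% | 82% | 65% |
| 0.7 | 78% | 51–52% | 97% | 46% |
| 0.8 | 96% | 89–90% | almost 100% | 10% |

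The mixed share is the at-least-one share minus the all-three share, for example 82 − 17 = 65. The rest-stress correlation hardly matters.

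With all 12 global versions at a true r of 0.6, and versions from one camera correlated 0.8 to 0.95 (assumed), all pass in 2 to 6% and at least one in 92 to 97%. This is an upper case, because it treats every version as an equal candidate.

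**Whether the versions are equal candidates.** Section 1.1 names the need for attenuation and scatter correction as a barrier to measuring flow with SPECT. It also says the pig data were corrected for both. Section 4.1 scales K1 to flow with the relationship from those pig studies. It sets out the kinetic analysis around the in-house package and brings in the commercial one at the end, as a comparison. In-house software with corrected images is therefore the natural main analysis, and the other versions read as secondary.

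**Whether the decision rule is open.** Hypotheses 1 and 3 list global and regional flow and flow reserve together. Read literally, all are expected to exceed 0.6. No passage supports success on any single one.

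**The case for a change.** The strongest case for a change is that the plan states a threshold and sizes the study around r = 0.6, so calling it exploratory does not excuse an undefined verdict. Even with the software and reconstruction settled by inference, rest flow, stress flow, flow reserve and the regions remain. The gap between 17% (all three) and 82% (any) at the planning value needs no choice of version. Naming one correlation would cost a sentence and no scans.

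Much of this stands. No section names a deciding correlation, and the inference about software and corrections is not a statement. The pig correlations in Section 1.1 (0.75 to 0.83 for flow, up to 0.89 for reserve) do not settle the human value: they are against simultaneous microspheres, whereas here the two scans may be up to 4 weeks apart.

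Three things limit it. A true r equal to the threshold is the least favourable setting, where even one named r passes only about half the time. The rise from one chosen r to any of three is about two-fold at a true r of 0.5 (24% to 51–52%), and it matters only under a rule the plan does not contain. Finally, the remedy cannot be completed from the documents: they give no ground for ranking rest flow, stress flow or reserve, and the one wording that can be supplied (separate states and regions, one pair per participant) is the reading that already fits the sample size.

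**Conclusion.** No change to the plan follows. This is missing detail in a small single-centre imaging comparison, and no stated number or rule is shown to be wrong. The n of 24 is correct for one correlation, and no claimed power is lost. Followed as written, the plan reports every correlation, so a reader will see which exceed 0.6 and which do not; a selective claim would be visible against hypotheses that name all the measures.

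The size of the ambiguity depends on the true r: three global verdicts are mixed in about 65% of trials at 0.6, 46% at 0.7 and 10% at 0.8. Those figures rest on the assumptions listed above and on 27 evaluable participants. Analysts can fill the gap by treating the in-house package with attenuation and scatter correction as the main analysis and reporting rest flow, stress flow and reserve separately. The remaining versions would then be supporting results.
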